2.0.1 Phase IIa safety Data

The number of subjects with TEAEs from Day -1 to 30 or 60 days after the last dosing was the same between all treatment groups: 6 (100.0%) patients in the 240 mg CD24Fc single dose cohort, 6 (100.0%) patients in the 480 mg CD24Fc single dose cohort, 6 (100.0%) patients in the 480/240/240 mg multiple dose cohort, and 6 (100.0%) patients who received placebo experienced TEAEs.

The most common TEAEs were stomatitis (6 [100.0%] patients in the 240 mg CD24Fc single dose cohort, 6 [100.0%] patients in the 480 mg CD24Fc single dose cohort, 5 [83.3%] patients in the 480/240/240 mg CD24Fc multiple dose cohort, and 6 [100.0%] patients who received placebo); platelet count decreased (6 [100.0%] patients in the 240 mg CD24Fc single dose cohort, 6 [100.0%] patients in the 480 mg CD24Fc single dose cohort, 5 [83.3%] patients in the 480/240/240 mg CD24Fc multiple dose cohort, and 5 [83.3%] patients who received placebo); white blood cell count decreased (6 [100.0%] patients in the 240 mg CD24Fc single dose cohort, 6 [100.0%] patients in the 480 mg CD24Fc single dose cohort, 5 [83.3%] patients in the 480/240/240 mg CD24Fc multiple dose cohort, and 4 [66.7%] patients who received placebo). Severe stomatitis (\geq Grade 3) occurred in 3 (50.0%) patients in the 240 mg CD24Fc single dose cohort, 4 (66.7%) patients in the 480 mg CD24Fc single dose cohort, 2 (33.3%) patients in the 480/240/240 mg CD24Fc multiple dose cohort, and 5 (83.3%) patients who received placebo, with a clear inverse correlation between CD24Fc doses and duration of severe stomatitis.

One (16.7%) patient in the 480 mg CD24Fc single dose cohort and 2 (33.3%) patients who received placebo experienced a study drug-related TEAE. The most common study drug-related TEAE was diarrhea (1 [16.7%] patient in the 480 mg CD24Fc single dose cohort and 2 [33.3%] patients who received placebo). No patients in other cohorts experienced a study drug-related TEAE.

The incidence of Grade 3/4/5 TEAEs was the same between all treatments: 6 (100.0%) patients in the 240 mg CD24Fc single dose cohort, 6 (100.0%) patients in the 480 mg single dose cohort, 6 (100.0%) patients in the 480/240/240 mg multiple dose cohort, and 6 (100.0%) patients who received placebo. One (16.7%) patient in the 480 mg CD24Fc single dose cohort experienced hyperglycemia that was considered a study drug-related Grade 3/4/5 TEAE.

In total, the incidence of TEAEs of white blood cell count decreased, lymphocyte count decreased, and neutrophil count decreased were higher in patients who received CD24Fc compared to patients who received placebo (white blood cells decrease 94% vs 67%, lymphocyte decrease 83% vs 50%, neutrophil decrease 89% vs 50%). The incidence of TEAEs of platelet count decreased was similar between patients who received CD24Fc and patients who received placebo (94% vs 83%).

No patient had a laboratory abnormality that was considered an SAE or resulted in discontinuation of study drug.

No patients who received either single or multiple dosing of CD24Fc had positive ADA results at any time point sampled pre- or post-infusion.

A TEAE of weight increased was reported by 1 (16.7%) patient who received placebo and a TEAE of weight decreased was reported by 3 (16.7%) patients who received CD24Fc. A TEAE of ECG QT prolonged was reported by 1 (16.7%) patient who received placebo.

Donor Cell Engraftment and Chimerism:

In total, 18 (100.0%) patients who received CD24Fc and 6 (100.0%) patients who received placebo experienced neutrophil engraftment. The median time to neutrophil engraftment was 13.5 days for patients in the 240 mg CD24Fc single dose cohort, 13.5 days for patients in the 480 mg CD24Fc single dose cohort, 13.0 days for patients in the 480/240/240 mg CD24Fc multi-dose cohort, and 15.5 days for patients who received placebo.

In total, 18 (100.0%) patients who received CD24Fc and 5 (83.3%) patients who received placebo experienced platelet engraftment. The median time to platelet engraftment was 15.5 days for patients in the 240 mg CD24Fc single dose cohort, 13.0 days for patients in the 480 mg CD24Fc single dose cohort, 12.0 days for patients in 480/240/240 mg CD24Fc multiple dose cohort, and 15.0 days for patients who received placebo. No patients experienced primary engraftment failure.

The mean CD3 cell chimerism on Day 28/Day 30 was 73.0% donor cells for patients who received CD24Fc and 77.4% donor cells for patients who received placebo. The mean CD3 cell chimerism on Day 100 was

80.9% donor cells for patients who received CD24Fc and 73.8% donor cells for patients who received placebo.

[figure not shown]
The mean CD33 cell chimerism on Day 28/Day 30 was 100.0% donor cells for patients who received CD24Fc and 100.0% donor cells for patients who received placebo. The mean CD33 cell chimerism on Day 100 was 99.4% donor cells for patients who received CD24Fc and 96.6% donor cells for patients who received placebo.

2.1 Pharmacokinetics in Humans

2.1.0 Phase I PK

The PK of CD24Fc in healthy human subjects was determined from the single dose Phase 1 study. The mean plasma concentration of CD24Fc increased proportionally to the dose of CD24Fc administered (Figure 10). For all dose groups except 120 mg, the maximum mean plasma concentration of CD24Fc was reached at 1 hour post-dose. The maximum mean plasma concentration of CD24Fc for the 120 mg group was reached at 2 hours post-dose. By Day 42 (984 hours), the mean plasma concentration of CD24Fc for all groups had decreased to between 2% and 4% of the maximum mean plasma concentration. The plasma CD24Fc reached T_{max} at 1.34 hours. The $t_{1/2}$ of plasma CD24Fc range was 280.83 to 327.10 hours.

Figure 10: Plot of Mean (\pm SD) Plasma CD24Fc Concentration by Treatment – PK Evaluable Population

PK = pharmacokinetic; SD = standard deviation.

Source: Investigators Brochure.

2.1.1 Phase IIa PK

The PK of CD24Fc in human subjects undergoing HCT has been determined from the Phase IIa study from the two single dose cohorts and one multi-dose cohort. With the 240 mg single dose, the mean plasma concentration of CD24Fc is similar to the 120 mg single dose in Phase I human volunteers. The 480 mg dose shows a proportional increase of CD24Fc at all time points ([Figure 11, upper panel](#)). The 480/240/240 mg multi-dose maintains the CD24Fc plasma concentration over 10,000 ng/ml over the period of Day-1 to Day 42 post-HCT ([Figure 11, lower panel](#)).

[figure not shown]
Following a single IV administration of CD24Fc (240 and 480 mg CD24Fc single dose cohorts), the geometric mean plasma exposure ($C_{max,1d}$, AUC_{0-42d} , and AUC_{0-inf}) increased with increasing CD24Fc doses. The mean $t_{1/2}$ and λ_z were similar between the 240 and 480 mg doses of CD24Fc. The mean values of $t_{1/2}$ were 414.739 and 406.648 h and the mean values of λ_z were 0.0018 and 0.0017 h^{-1} for the 240 and 480 mg CD24Fc single dose cohorts, respectively. Additionally, there was an increase in the mean V_z and CL between the 240 and 480 mg doses of CD24Fc.

Following multiple IV administrations of CD24Fc (480/240/240 mg CD24Fc multi-dose cohort), the exposure of CD24Fc was sustained over time. Additionally, the mean plasma CD24Fc concentration on Day 100 was higher for the 480/240/240 mg CD24Fc multi-dose cohort (850.84 ng/mL) compared to the single dose cohorts (216.38 ng/mL and 330.96 ng/mL for the 240 and 480 mg CD24Fc single dose cohorts, respectively). Furthermore, the geometric mean $AUC_{0-last,overall}$ value was higher for the 480/240/240 mg CD24Fc multi-dose cohort (37,363,953.5 ng·h/mL) compared to the single dose cohorts (10,156,549.9 ng·h/mL and 15,522,686.2 ng·h/mL for the 240 and 480 mg CD24Fc single dose cohorts, respectively).

The median $t_{max,1d}$ (2.10 h for both the 240 and 480 mg CD24Fc single dose cohorts and 2.13 h for the 480/240/240 mg CD24Fc multiple dose cohort) remained consistent across all of the CD24Fc doses. For the 480/240/240 mg CD24Fc cohort, the median $t_{max,1d}$ and $t_{max,28d}$ were similar (2.13 and 2.52 h, respectively).

Figure 11: Plot of Mean (\pm SD) Plasma CD24Fc Concentration by Treatment – PK Evaluable Population.

(Upper). Single dose cohorts, 240mg (n=6); 480mg (n=6). (lower). multi-dose cohort. 480-240-240mg (n=6).

2.2 Immunogenicity in Humans

2.2.0 Phase 1 ADA

Serum samples in the Phase I study were screened for anti-drug antibodies. Anti-CD24Fc antibodies were detectable at Day 28 and Day 42 in 1 subject in each of the 5 dose cohorts; however, for the subject in the CD24Fc 120 mg group and the subject in the CD24Fc 240 mg group, anti-CD24Fc antibodies were also detectable pre-dose at levels higher than post-dose levels. Except for those subjects with significant pre-dose anti-CD24Fc antibody levels, all post-dose anti-CD24Fc antibody levels were modest. No deviations in PK were found in any subjects with detectable anti-CD24Fc antibody levels.

2.2.1 Phase IIa ADA

In the Phase IIa allogeneic HCT context, given the immunoablation and immunosuppression of host immunity at time of CD24Fc administration, ADA responses were monitored but unlikely to be elicited.

For the two single dose cohorts, the samples were collected at 7 time points from Day-1 to Day 100. For the multi-dose cohort, the samples were collected at 13 time points from Day-1 to Day 100. All samples are negative for ADA in the Phase IIa study.

3. STUDY MEDICATION

3.0 Study drug: CD24Fc or CD24 IgG (OncoImmune, Inc.) and placebo

CD24Fc (CD24 IgG) is a fusion protein consisting of the extracellular domain of mature human CD24 linked to the human immunoglobulin G1 (IgG1) Fc domain.

The placebo is 0.9% Sodium Chloride Solution for IV infusion.

3.0.0 Molecular Formula and Formulation

The complete molecular formula of CD24Fc has not been determined at this time. The mature protein is 261 amino acids long and each CD24Fc molecule includes the 30 amino acid CD24 extracellular domain. CD24Fc forms a disulfide-linked homodimer with a predicted mass of 57.7 kilodaltons (kDa) based on the homodimer amino acid sequence. However, the apparent molecular weight of the intact dimer is approximately 80 KDa based on non-reduced SDS-PAGE. The CD24 domain is highly glycosylated with both N-linked and O-linked oligosaccharides, which comprise approximately 80% of the mass of the CD24 domain.

Name	CD24Fc for IV infusion.
Vial content	120mg/12mL
Formulation	Liquid formulation for IV infusion.
Route	IV Infusion
Storage	-20°C, avoid light.
Manufacturer	Catalent, Inc.
Provider	OncoImmune, Inc

3.0.1 Packaging, Ordering, and Inventory Management

CD24Fc is supplied in clear borosilicate glass vials with chlorobutyl rubber stoppers and aluminum flip off seals. Drug product vials are stored at OncoImmune's clinical distribution site, ALMAC Clinical

Services, at [name]. Study site (UCDCC) IDX pharmacy will order the drug for onsite storage after the study activation.

Availability, Storage and Stability

CD24Fc is supplied as a sterile, clear, colorless, preservative-free aqueous solution for parenteral administration. CD24Fc will be stored at -20° C until removed for use. Remove the CD24Fc vials from the freezer and thaw immediately prior to dose preparation. The CD24Fc infusion should begin within 3 hours after reconstitution.

3.0.2 Administration

CD24Fc at doses of 480 mg or 240 mg will be prepared in a diluent comprising 0.9% Sodium Chloride in a volume of 100 ml and be administrated by intravenous infusion over a minimum of 60 minutes as specified in Section 6.2

3.0.3 Disposal and Destruction

Responsibility for drug accountability is on the investigator and the assigned pharmacist or designee. Drug supply will be disposed of according to institutional standard operating procedures. Accurate records of all investigational product received at and dispensed from the study site should be recorded on the Drug Log.

4. TOXICITIES MONITERED

4.0 Treatment-Related Toxicities

The toxicity scale, definitions, and specific criteria for each toxicity level will be those as outlined in the guidelines defined by the NCI CTCAE version 5.0. ([Appendix 4](#)). If the patient develops any grade 3 or greater hematologic or non-hematologic toxicity that is possibly, probably, or definitely related to the CD24Fc, no further drug administration will be given to that patient and the patient will be removed from protocol therapy (see Section 4.1). Treatment delay within 3 scheduled days is allowed. Dose modification based on the renal and hepatic function values and hematologic laboratory values (see Section 6.4).

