4.2 Managing Infusion Reactions

Although infusion reactions were not observed in the Phase 1 and Phase IIa clinical trials, there is a theoretical potential for CD24Fc to result in infusion reaction. CD24Fc, which includes a human portion IgG1 may induce Fc γ R cross-linking, which has been associated with infusion reactions for some therapeutics.

Supportive care and vitals monitoring (including but not limited to supplemental oxygen, diphenhydramine, acetaminophen, ibuprofen, steroids and fluids) in the event of infusion reaction will be allowed and be dictated per institutional standards and policies. Depending on the severity of the infusion reactions, patient might be resumed the study drug at the discrepancy of the treatment physician. Patient will be permanently discontinued from the study if infusion reactions recur despite of pre-medications.

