6.4.2 Hematologic laboratory values

CD24Fc will be administered on the scheduled day if absolute neutrophil count (ANC) $\geq 1,000$ / μ L, hemoglobin ≥ 8 gm/dL and a pretreatment platelet count of $\geq 75,000$ / μ L.

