6.4.3 Dose adjustment

There should be a one level dose reduction (i.e., CD24Fc 240 mg on day 1, 120 mg on day 14, and 120 mg on day 28 i.v.) if any \geq G3 hematologic due to CD24Fc that requires < 2 week to recover to grade 1 or less. There will be no dose reduction according to irAEs.

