6.7 Criteria for Removal from Protocol Treatment

- Unacceptable toxicity (as determined by the treating physician and/or the patient), or toxicity requiring discontinuation of treatment (See sections 4.0 and 4.1).
- Elevation in AST or ALT $>20x$ ULN on bloodwork prior to CD24Fc treatment.
- Elevation of total bilirubin $>5x$ ULN on bloodwork prior to CD24Fc treatment.
- If the recovery of any $\geq G3$ hematologic or non-hematological toxicity due to CD24Fc to grade 1 or less requires > 2 weeks.
- Patients may choose to withdraw from the study at any time for any reason.
- Patients may be withdrawn from the protocol at the investigator's discretion if the investigator feels that continuation is not in the patient's best medical interest or if the patient is non-compliant with treatment.
- Completion of treatment CD24Fc.
- All reasons for discontinuation of treatment must be documented in the case report forms.
- Therapy after Protocol Treatment is stopped: If patients fail to respond to the protocol treatment and/or are removed from the therapy because of toxic effects or "disease progression", further treatment, if any, is at the discretion of the investigator.

Follow-up off Protocol Treatment: After removal from protocol treatment, all patients will be followed for late toxicities. Patients will be seen 4 weeks, 4 months and 7 months after coming off therapy. If ongoing toxicities have not resolved to \leq grade 1 within the first 4 weeks, patients are to be seen every month until toxicity resolves to \leq grade 1. No new toxicities after the 4-week follow-up will be re-reported unless considered related to protocol treatment by the investigator.

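### Sections 4.0 and 6.4.3 give opposite instructions for a CD24Fc-related grade 3 or higher hematologic toxicity that recovers in under 2 weeks

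*Combined protocol and SAP*

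**What the plan says.** - **Section 4.0** covers grade 3 or higher toxicity, hematologic or non-hematologic, that is "possibly, probably, or definitely related to the CD24Fc". The action is mandatory: "no further drug administration will be given to that patient and the patient will be removed from protocol therapy". Recovery time plays no part. The section's last sentence refers to 6.4 for dose modification on renal, hepatic and hematologic values.
- **Section 6.4.3** prescribes a one-level reduction for a grade 3 or higher event described as "hematologic due to CD24Fc that requires < 2 week to recover to grade 1 or less". The reduced level is given as "CD24Fc 240 mg on day 1, 120 mg on day 14, and 120 mg on day 28".
- **Section 6.7** lists grounds for removal. The first bullet includes "toxicity requiring discontinuation of treatment (See sections 4.0 and 4.1". A later bullet applies where the recovery of any grade 3 or higher "hematologic or non-hematological toxicity due to CD24Fc to grade 1 or less requires" more than 2 weeks.
- **Section 4.2** states: "Depending on the severity of the infusion reactions, patient might be resumed the study drug". The decision is left to the physician and no grade is named. Permanent discontinuation is required only if reactions recur despite pre-medication.
- **Sections 6.4.2 and 6.3** condition each dose on neutrophil, hemoglobin and platelet thresholds, and omit a missed dose that cannot be rescheduled within 3 days.

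**The concern.** A patient with a grade 3 fall in neutrophils, judged due to CD24Fc and recovered within 10 days, meets both rules. Under 4.0 the patient is off protocol therapy. Under 6.4.3 the patient receives the next dose at a reduced level. Two investigators could take opposite actions and each could cite the protocol. This would affect drug exposure, what is reported as a protocol deviation, and the count of discontinuations for toxicity. Attribution in Phase II is made blind, so placebo patients can meet these rules too.

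**Working it through.** No figure in the plan is in dispute. The check compares the rules, then asks when and how often the conflict could arise.

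**Step 1. One related grade 3 event under each rule.**

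| Event | 4.0 | Other text | Result |
|---|---|---|---|
| Hematologic, recovers in under 2 weeks | Remove | 6.4.3: reduce and continue. 6.7: recovery bullet not met, first bullet leads back to 4.0 | Direct contradiction |
| Non-hematologic, recovers in under 2 weeks | Remove | 6.7: recovery bullet not met, first bullet leads back to 4.0 | Inconsistent by implication |
| Either type, recovery over 2 weeks | Remove | 6.7: remove | No conflict |
| First infusion reaction, grade 3 | Remove | 4.2: resumption depends on severity, no grade given | Compatible if 4.2 means below grade 3, but it does not say so |

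**Step 2. Does attribution separate the rules?** No. An event due to CD24Fc is also at least possibly related to it. Every 6.4.3 event is therefore a 4.0 event, and the stronger attribution carries the milder action.

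**Step 3. Does any text set precedence?** Section 4.0 also refers to 4.1, but 4.1 defines Phase I DLTs and does not say who may continue dosing. The pointer from 4.0 to 6.4 is not worded as an exception, and 4.0 names hematologic toxicity expressly. Section 6.7 points back to 4.0 while carrying a 2-week criterion that does nothing if 4.0 already removes everyone.

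**Step 4. When can it arise?** A dose must remain, so the event must follow dose 1 or dose 2. The day-28 window closes on day 28 + 3 = 31. An event that takes 13 days to recover must begin by day 31 - 13 = 18.

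**Step 5. How often?** The plan gives no rate. The prior-trial summaries in 1.4 and 2.0, as available here, allow a rough bound.
- CD24Fc recipients: 40 - 10 = 30 healthy volunteers (the 10 on placebo follow from 6 subjects being 60.0%), 18 in Phase IIa and 20 in the expansion cohort, total 68. On the present three-dose regimen: 6 + 20 = 26.
- Grade 3 or higher hematologic events attributed to CD24Fc: none. One related non-hematologic event of that severity is reported (hyperglycemia).
- One-sided 95% upper limit for 0 of n is 1 - 0.05^(1/n): 4.3% for n = 68 and 10.9% for n = 26. With 6 + 36 = 42 planned CD24Fc recipients, that is 0 to 1.8 or 0 to 4.6 patients. Events recovering in under 2 weeks are a subset.
- The zero depends on attribution. Section 1.4.1 reports grade III-IV neutrophil decrease in 83.3% on CD24Fc and 50% on placebo (15/18 vs 3/6), ascribed to conditioning. With 18 events in 24 patients, the observed table has probability C(18,3) x C(6,3) / C(24,6) = 816 x 20 / 134,596 = 0.121. The less likely tables add 0.017 + 0.001, so the two-sided Fisher p is 0.14.

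**The case against.** The strongest reply is that 4.0 itself sends the reader to 6.4 for hematologic values, so 6.4.3 is the specific rule and 4.0 the general one. That may well be the intent. It does not settle the text, because 4.0 lists hematologic toxicity among the events that end treatment and makes no exception.

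A reader might infer that 6.7 permits continued dosing after a quick recovery. It does not. It is a list of removal grounds, it does not confine removal to slow recoveries, and its first bullet brings in 4.0. The point against it is only that one of its bullets has no function.

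A reader might also infer that 4.2 contradicts 4.0. The reference to severity can be read as covering reactions below grade 3, which agrees with 4.0. What remains is a missing grade limit.

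The practical risk is also contained. The study is run at one cancer center, and patients on treatment are discussed weekly (13.1). Section 6.4.2 requires adequate neutrophils, hemoglobin and platelets on the dosing day. Sections 6.7 and 6.8 point to removal for a DLT, and 4.1 makes grade 4 hematologic toxicity a DLT in Phase I. These points stand and limit the consequences. They do not say which instruction applies.

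**Conclusion.** The contradiction between 4.0 and 6.4.3 is real and can be read from the current text. It covers related grade 3 or higher hematologic toxicity that recovers to grade 1 or less in under 2 weeks while a dose remains. Section 6.7 adds an inconsistency by implication, and 4.2 needs a grade limit.

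Severity is minor to moderate. The frequency is unknown and may be zero. The upper limits above come from healthy volunteers and transplant recipients, not from patients with irAEs, so they indicate scale only.

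Two stronger readings are not supported. The documents do not show that patients are in immediate danger, given the dosing-day thresholds. Nor do they show a CD24Fc effect on severe cytopenia: the larger neutrophil contrast of 89% vs 50% in the Phase IIa laboratory summary is not restricted to grade 3 or higher, and the grade III-IV comparison is inconclusive at p = 0.14. Stated power, sample size and stopping boundaries do not change.

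**What to change.** Give each event one action. The clinical team should choose between two options.

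- **Option A: 4.0 prevails.** Delete 6.4.3 and the over-2-week bullet of 6.7. The cost is that patients who recover quickly forgo their remaining doses.
- **Option B: a worded exception.** Amend 4.0 to except grade 3 hematologic toxicity that is not a DLT under 4.1 and recovers to grade 1 or less within 2 weeks. Limit 6.4.3 to grade 3, and write the reduction for the doses still to come (120 mg on day 14 and/or day 28). Keep removal for related grade 4 hematologic and related grade 3 or higher non-hematologic toxicity. Align the over-2-week bullet of 6.7 with this, and use one attribution wording in 4.0 and 6.4.3. The cost is re-exposing these patients at 120 mg.

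Under either option, state in 4.2 that resumption applies only to infusion reactions below grade 3. The change is amendment wording, with no new visits, tests or patients.
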